11.1	Regulatory and ethical compliance	19
11.2	Responsibilities of the investigator and IRB	19
12	References	20

List of abbreviations/definitions

AE	Adverse Event
ASCVD	Atherosclerotic Cardiovascular Disease
eCRF	Electronic Case Report Form
dL	Deciliter
GCP	Good Clinical Practice
mg	milligram(s)
OTC	Over the Counter
SAE	Serious adverse event
Study Medication	Study medication refers to FDA approved rosuvastatin
Supplement	Refers to over the counter fish oil, cinnamon, garlic, turmeric, plant sterol
Sponsor	Cleveland Clinic

1 Introduction

1.1 Background

Few well-controlled trials have studied the LDL-lowering effects of dozens of marketed “cholesterol health” dietary supplements. These products combine for sales of billions of dollars annually, primarily via online marketing. The business model for the dietary supplement industry often relies on efforts to undermine FDA-approved cholesterol lowering medications in favor of “all natural” alternatives for “heart protection” and “cholesterol management.” Marketing of dietary supplements (without evidence of benefit) is protected by the Dietary Supplement Health and Education Act of 1994, which assigns oversight of this industry primarily to the Federal Trade Commission, rather than the Food and Drug Administration. The supplement industry markets against prescription statins on eCommerce platforms, but rarely, if ever, perform comparative studies. Furthermore, prior research suggests most U.S. consumers believe cholesterol health supplements are safer than statins, and a majority of the public also believe supplements are as effective, or more effective, than prescription statins. Approximately one third of US adults who have been told they have elevated cholesterol are using a supplement to provide heart health protection rather than a statin. This represents a significant public health concern.¹⁻⁶

1.2 Purpose

The purpose of this study is to evaluate the effect of select dietary supplements on cholesterol health compared with a low dose of a statin.

2 Objectives and endpoints

Primary Objective

The primary objective of this study is to compare the LDL lowering of rosuvastatin with the effect of six commonly used dietary supplements on cholesterol health

Secondary Objective

Assess the effect of each supplement on inflammatory markers compared with rosuvastatin 5 mg.

Primary Endpoint

The percent change in LDL-C for rosuvastatin 5 mg compared with dietary supplements after 4 weeks.

Secondary Endpoints

- The percent change in high sensitivity C reactive protein (hsCRP) for rosuvastatin 5 mg and dietary supplements compared with placebo after 4 weeks.
- The percent change in HDL-C, total cholesterol, and triglycerides for each supplement compared with rosuvastatin.
- The percent change in HDL-C, total cholesterol, and triglycerides for each supplement compared with placebo.

3 Study design

A randomized, single blind study design will be used to evaluate rosuvastatin 5 mg. vs. placebo and 6 commercially available over the counter supplements in a hierarchical testing order. Each participant will take study medication/supplement for a total of 4 weeks.

3.1 Rationale for duration of administration

The duration of 4 weeks is sufficient as steady-state LDL-C levels are reached for rosuvastatin 5mg within two weeks.

3.2 Risks and benefits

The risks may include a lack of effect on cholesterol health with supplements over a short duration, or an adverse effect of one of the study medication/supplements. Undeclared ingredients are a possibility with over-the-counter supplements.

The benefits may include the potential to have an effect on cholesterol health with one or more of the study medication/supplements.

4 Population

The study will randomize primary prevention patients who are considered borderline and intermediate risk for ASCVD based upon the 2018 Cholesterol Treatment Guidelines⁷ and are not taking any of the studied medication/supplements at the time of randomization.

4.1 Inclusion criteria

Subjects eligible for inclusion in this study must meet **all** of the following criteria:

1. Written informed consent must be obtained before any assessment is performed.
2. U.S. adults with primary hypercholesterolemia, 40-75 years of age.
3. Not currently taking statins or one of the dietary supplements included in the trial. Patients willing to discontinue a prohibited supplement for 4 weeks prior to enrollment will be allowed to participate.
4. LDL-cholesterol between 70 and 189 mg/dL.
5. Patients without diabetes mellitus and a 10-year risk of ASCVD between 5 and <20% using the pooled cohort risk equation. *

Or

Patients with diabetes mellitus in females 50-60 years of age or males 40-50 years of age with an LDL-C between 70-189 mg/dL and with an ASCVD risk below 20%.

*<http://tools.acc.org/ASCVD-Risk-Estimator-Plus/#!/calculate/estimate/>

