4.2 Exclusion criteria

Subjects meeting any of the following criteria are not eligible for inclusion in this study:

1. Age < 40 or >75 years of age
2. Women who are pregnant, plan to become pregnant within the next 6 months, or are breastfeeding.
3. Documented liver dysfunction or history of elevated LFTs indicating active liver disease
4. Documented chronic renal dysfunction within the past two years defined as an $eGFR \leq 30 \text{ mL/min/m}^2$.
5. Known hypersensitivity to rosuvastatin or any supplement under investigation (i.e. shellfish allergy, etc.).
6. Currently taking any prescription statin, or other prescription medication/supplements to treat elevated cholesterol or triglycerides.
7. Currently taking a medication/supplement that has known interaction with rosuvastatin, including fenofibrate, gemfibrozil, HIV medications, colchicine, cyclosporine, warfarin, anti-viral medications to treat Hepatitis C, regorafenib, and darolutamide.
8. Are unwilling to discontinue prohibited dietary supplement(s) for 4 weeks prior to participation or during the course of the trial. Other non-prohibited supplements will be permitted if doses have been stable for at least 4 weeks.
9. Known cardiovascular disease including a history of prior MI, stroke/TIA, PAD or prior revascularization procedures of the heart or vasculature (e.g. CABG, stenting, PCI etc.).
10. Fasting Triglycerides >200mg/dl.
11. In the opinion of the investigator, any other condition that will preclude participation in the study.

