4.3.4 Prohibited medication/supplement and therapies

New use of prescription medication/supplements for elevated cholesterol or triglycerides during participation in the trial.

New use of over the counter dietary supplements marketed for cholesterol health or triglyceride health for 4 weeks prior to or during participation in this study are prohibited. Chronic use of supplement types other than those being assessed in the trial will be permitted if doses have been stable for 4 weeks or longer.

Patients will be encouraged to maintain lifestyle habits present at the time of trial enrollment during the course of the trial. Significant dietary and physical activity modifications will be discouraged over the 4 weeks of participation. Participants are not to enroll in weight loss programs during the trial.

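### Trial supplements carry a 4-week off-period before entry, but statins and other prescription lipid drugs are tested only for current use, so a recent stopper can enter with a drug-suppressed baseline LDL-C

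*Protocol*

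**What the plan says.** **Supplements.** Inclusion 3 (Protocol 4.1) sets an off-period: "Patients willing to discontinue a prohibited supplement for 4 weeks prior to enrollment will be allowed to participate". Exclusion 8 (Protocol 4.2) mirrors it by excluding people who "Are unwilling to discontinue prohibited dietary supplement(s) for 4 weeks prior to participation or during the course of the trial".

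**Statins and prescription lipid drugs.** Inclusion 3 requires that patients are "Not currently taking statins or one of the dietary supplements included in the trial". Exclusion 6 covers patients "Currently taking any prescription statin, or other prescription medication/supplements to treat elevated cholesterol or triglycerides". Section 4 (Population) describes patients who "are not taking any of the studied medication/supplements at the time of randomization". All three are in the present tense and none has a look-back.

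**Related provisions.**
- Protocol 4.3.4 prohibits "New use of prescription medication/supplements for elevated cholesterol or triglycerides during participation in the trial", which does not reach back before entry.
- The entry range is "LDL-cholesterol between 70 and 189 mg/dL", with no condition that it be measured off drug.
- Baseline is the Day 0 draw or a fasting panel taken within 4 weeks of screening (Protocol 6, SAP 6.3.2).
- Protocol 4.3.3 records the class of prior medication, but no stop date is requested. The medication list in SAP 7.6 has no lipid-lowering class.
- The primary model adjusts at least for baseline LDL-C and age (SAP 8.1).

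**The concern.** The primary endpoint is percent change from baseline, so it depends on a baseline that reflects the patient's untreated LDL-C. Someone who stopped a statin shortly before the baseline panel meets every written criterion, yet the measured baseline may still be partly on drug. As that effect wears off, LDL-C rises for a reason unrelated to the assigned product.

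Three things are at stake. A few large positive changes widen the SD beyond the planned 15. With 25 per arm, one stopper more in one arm than in another moves a mean noticeably. Within-arm changes shift upward, so an inert supplement can appear to raise LDL-C, and a real lowering can be pulled back below the 15% level at which Protocol 4.3.5 calls for impurity testing. Because the primary comparisons form a fixed sequence, one step lost to added variance makes every later step exploratory.

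**Working it through.** **1. The plan's own figure.** Inputs from Protocol 4.3.2 and SAP 3.3: difference 15, SD 15, alpha 0.05 (two-sided per Protocol 10.5), 25 per group. The standardized difference is 15/15 = 1. A two-sample t-test needs 22.02, so 23 per group, for 90% power; at 25 per group the power is 93.4%. The planned size is adequate, and 93% is the reference below.

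**2. One recent stopper.** Let B be the off-drug LDL-C, L the fraction by which the earlier drug still suppresses baseline, and p the percent change the patient would show without that history. Baseline is (1-L)B. If the earlier drug has worn off by Day 28, the final value is (1+p/100)B, so

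observed change = 100 × [(1+p/100)/(1-L) - 1].

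| L (assumed) | 1/(1-L) | p = 0 (inert product) | p = -15 | p = -35 |
|---|---|---|---|---|
| 25% | 1.33 | +33 | +13 | -13 |
| 35% | 1.54 | +54 | +31 | 0 |
| 45% | 1.82 | +82 | +55 | +18 |

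**3. Expected difference between arms.** With k stoppers in each arm of 25 and true difference d, the expected difference is d × [1 + (k/25) × (1/(1-L) - 1)].
- d = 15, k = 1: 15.2, 15.3 or 15.5.
- d = 35, k = 1: 35.5, 35.8 or 36.2.

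The between-arm shift is about one point or less.

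**4. Chance imbalance.** One extra stopper in an inert arm moves its mean by 33.3/25 = 1.3, 53.8/25 = 2.2 or 81.8/25 = 3.3 points, which widens the apparent advantage of rosuvastatin. One extra stopper in a rosuvastatin arm with p = -15 moves that mean by (13.3+15)/25 = 1.1, (30.8+15)/25 = 1.8 or (54.5+15)/25 = 2.8 points, which narrows it.

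**5. Variance.** With one stopper in an inert arm, the expected sample variance is [24×15² + (15/(1-L))²]/25 + (shift)²/25, where shift is the p = 0 column above.
- L = 25%: 232.0 + 44.4 = 276.4, SD 16.6.
- L = 35%: 237.3 + 116.0 = 353.3, SD 18.8.
- L = 45%: 245.8 + 267.8 = 513.5, SD 22.7.

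**6. Power.** Simulated two-arm comparisons, 25 per arm, SD 15, equal numbers of stoppers in both arms:

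| True difference | Stoppers per arm | L = 25% | L = 35% | L = 45% |
|---|---|---|---|---|
| 15, t-test | 0 | 93% | 93% | 93% |
| 15, t-test | 1 | 91% | 87% | 75% |
| 15, t-test | 2 | 89% | 79% | 58% |
| 35, t-test | 1 or 2 | about 100% | about 100% | about 100% |

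Repeat runs differ by about a point; the 75% entry ranged from 74% to 76%. With a Mann-Whitney test at a difference of 15, power is about 83% to 91% across the same one- and two-stopper scenarios.

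**7. Does baseline adjustment help?** With an assumed baseline mean of 130 and SD of 25, ANCOVA on baseline gives 91%, 86% or 76% with one stopper per arm and 88%, 80% or 66% with two. It recovers little, because a suppressed value and a naturally low value look alike to the model.

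**The case against.** **Frequency and timing are unknown.** The documents give no count of recent stoppers; one per arm already means 8 of 200 patients. The only timing statement, in Protocol 3.1, is that "steady-state LDL-C levels are reached for rosuvastatin 5mg within two weeks". That is onset, not offset. If offset is equally quick, only patients who stopped within about two weeks of the baseline panel matter. This stands: the size of the problem is conditional, though the gap in the criteria is not.

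**The asymmetry has a reason.** Supplement users are invited to stop in order to enter, so they need an off-period; statin users are simply excluded. This explains the wording but leaves people who had already stopped uncovered.

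**There are partial safeguards.** Exclusion 11 lets an investigator decline such a patient, prior medication class is recorded, further adjustment is possible where factors differ significantly across groups, and a non-parametric test replaces ANCOVA if the distribution looks non-normal. The last would recover most of the worst-case power loss, although the plan names no test and relies on a graphical judgement. None of these requires that recent users be kept out or identified.

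**A stronger reading.** From the single-patient contrasts (47, 54 or 64 points where the true effect is 35), a reader might infer that the trial's rosuvastatin effect is systematically inflated. The documents do not support that: allocation is random, and with one stopper per arm a 35-point difference becomes only about 35.5 to 36.2. A reader might also infer that the trial is underpowered. That holds only if the true difference is near the planned 15, stoppers are present, suppression is large and the parametric test is kept.

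**Conclusion.** The gap is real and nothing in either document closes it: as written, the criteria admit a patient with a drug-suppressed baseline into a trial whose endpoint is percent change. The consequence is added variance, chance imbalance and distorted within-arm estimates, not systematic bias between arms. At the planned 15-point difference the t-test loss runs from about 2 points (L = 25%, one stopper per arm) to about 35 points (L = 45%, two per arm). These figures rest on assumed values of L, assumed numbers of stoppers and an assumed complete loss of the earlier drug's effect by Day 28. Confidence is high in the wording gap and low in how often it would matter. It is worth correcting because the correction is cheap.

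**What to change.** - Reconcile inclusion 3, exclusion 6 and Section 4 with the supplement criteria by adding a look-back for statins and other prescription lipid drugs. Count it back from the lipid panel actually used as baseline, since that panel may pre-date screening. The sponsor should set its length.
- Word it as an exclusion of recent users, not as an instruction or invitation to stop prescribed treatment.
- Record the date of last lipid-drug use in the eCRF.
- Add lipid-lowering drugs to the prior-medication list in SAP 7.6, so that any affected patients can be identified.

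Cost: one wording amendment, one eCRF date field and one line in the SAP. A few recent stoppers would be excluded.

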4.2 Exclusion criteria

Subjects meeting any of the following criteria are not eligible for inclusion in this study:

1. Age < 40 or >75 years of age
2. Women who are pregnant, plan to become pregnant within the next 6 months, or are breastfeeding.
3. Documented liver dysfunction or history of elevated LFTs indicating active liver disease
4. Documented chronic renal dysfunction within the past two years defined as an $eGFR \leq 30 \text{ mL/min/m}^2$.
5. Known hypersensitivity to rosuvastatin or any supplement under investigation (i.e. shellfish allergy, etc.).
6. Currently taking any prescription statin, or other prescription medication/supplements to treat elevated cholesterol or triglycerides.
7. Currently taking a medication/supplement that has known interaction with rosuvastatin, including fenofibrate, gemfibrozil, HIV medications, colchicine, cyclosporine, warfarin, anti-viral medications to treat Hepatitis C, regorafenib, and darolutamide.
8. Are unwilling to discontinue prohibited dietary supplement(s) for 4 weeks prior to participation or during the course of the trial. Other non-prohibited supplements will be permitted if doses have been stable for at least 4 weeks.
9. Known cardiovascular disease including a history of prior MI, stroke/TIA, PAD or prior revascularization procedures of the heart or vasculature (e.g. CABG, stenting, PCI etc.).
10. Fasting Triglycerides >200mg/dl.
11. In the opinion of the investigator, any other condition that will preclude participation in the study.

4.3 Study medication/supplements

4.3.1 Study medication/supplement groups

Eight groups will be studied, Rosuvastatin 5 mg compared with the following:

1. Placebo (comparable to rosuvastatin 5mg)
2. Fish oil (Nature Made™ 2 soft gels / day)
3. Cinnamon (1200mg, 2 capsules / day)
4. Garlique™ (1 tablet / day)
5. Turmeric (Bio Schwartz Turmeric Curcumin, 1500mg, 3 capsules / day)
6. Plant sterol (Nature Made CholestOff™ Plus, 2 soft gels 2x / day)
7. Red yeast rice (Arazo Nutrition, Red Yeast Rice, 1200mg, 2 capsules / day)

4.3.2 Medication/supplement study groups

Eligible subjects will be randomized 1:1:1:1:1:1:1 to the study groups in a blinded fashion. There will be 25 subjects per study group. The total sample size will be 200 patients.

Sample Size and Power

Assuming a common standard deviation of 15 and an alpha of 0.05, enrolling a total of 25 in each group will have 90% power to detect an average difference in percent change in LDL of 15 between rosuvastatin and each study group.

4.3.3 Concomitant therapy

Medication/supplement classification used by the subject prior to randomization will be recorded in the eCRF pages.

4.3.4 Prohibited medication/supplement and therapies

New use of prescription medication/supplements for elevated cholesterol or triglycerides during participation in the trial.

New use of over the counter dietary supplements marketed for cholesterol health or triglyceride health for 4 weeks prior to or during participation in this study are prohibited. Chronic use of supplement types other than those being assessed in the trial will be permitted if doses have been stable for 4 weeks or longer.

Patients will be encouraged to maintain lifestyle habits present at the time of trial enrollment during the course of the trial. Significant dietary and physical activity modifications will be discouraged over the 4 weeks of participation. Participants are not to enroll in weight loss programs during the trial.

4.3.5 Study group assignment, randomization

Randomization will occur using REDCap Cloud electronic database platform. Study medication/supplement will be dispensed by the investigational pharmacy in a blinded fashion for in person visits to study personnel or shipped to the subjects by the investigational pharmacy following randomization. Day 1 of the study is the first day that subjects start study medication/supplement. In the event that study medication/supplement is shipped to subjects, study personnel will verify the start of study medication/supplement (Day1) for medication/supplement accountability.

The study medication/supplement will be supplied from commercially available products and administered according to the package insert. The rosuvastatin 5mg and placebo will be provided by Astra Zeneca. The over the counter supplements will be purchased and due to documented history of supplement tainting, supplements may be tested for unlabeled enhancing impurities retrospectively if deemed necessary per data findings. If we observe > 15% lowering in LDL cholesterol, we will test for impurities.

4.4 Study group blinding

Subjects, investigator staff, persons performing the assessments, and the clinical trial team will be blinded to assigned study group. Baseline laboratory values will not be blinded to the subjects, investigator staff, and the clinical team. Additional lipid labs will be prohibited for the 4 week participation period. The Day 28 labs will not be blinded.

It is expected that the need for unblinding of a patient's study group will be extremely rare. Every effort should be made to preserve the blind unless there is a compelling reason that knowledge of the specific treatment would alter the medical care of the patient.

5 Informed consent procedures

Eligible subjects may only be included in the study after providing IRB approved informed consent. Informed consent must be obtained before conducting any study-specific procedures. Subjects will be prescreened using historical laboratory values within 13 months of screening prior to consenting. Subjects that screen fail will not be eligible for rescreening.

6 Visit schedule and assessments

Subjects should be seen for all visits/assessments as outlined in the assessment schedule. The baseline and final visits will be completed in-person or remotely.

The fasting lipid draw and complete metabolic panel (CMP) at Day 0 and Day 28 must be obtained from a Cleveland Clinic lab. Recently acquired lipid labs and complete metabolic panel may be used in place of a Day 0 lab draw if acquired within 4 weeks of screening at a Cleveland Clinic lab and performed in the fasting state. Subjects are to remain on study medication/supplement until Day 28 labs are drawn.

Study personnel will use the following historical information to input into the ASCVD risk calculator to determine eligibility:

- Age
- Gender
- Race
- Systolic blood pressure
- Diastolic blood pressure
- Treatment for high blood pressure and diabetes
- Current smoking status

If a historical blood pressure is not found within 1 year of screening, patient reported is acceptable.

Lipid panel, hs-CRP will be collected at the initial visit and Day 28.

- Lipids: Indirect **LDL-C** (Total Cholesterol, HDL-C, and Triglycerides)
- Inflammatory markers: **hs-CRP**

Table 7-1 Assessment Schedule

Activity	Study Day	
	Day 0 ^b	Day 28 ^{b,f} +4/-4 days
Informed consent obtained ^b	X	
Demographics	X	
Medical history	X	
Eligibility confirmed & subject randomized ^h	X	
Body weight ^g	X	
Height ^g	X	
Concomitant Medication/supplements	X	X
Hs-CRP	X	X
CMP, LDL-C, TC, HDL-C, and TG ^{c,d}	X	X
Pregnancy test ^a	X	
Study medication/supplement dispensed ⁱ	X	
Adverse events		X
Study medication/supplement adherence ^e		X

^a Females of child-bearing potential only, urine or serum at investigator's discretion.

^b The baseline (0) and 28 Day visit may be completed remotely. Consent will be obtained prior to completion of the baseline visit and may be completed remotely in accordance with Cleveland Clinic guidelines

^c Fasting lipid panel and complete metabolic panel should be drawn at a Cleveland Clinic lab facility. Patients should fast for approximately 8 hours.

^d Recently acquired lipid and complete metabolic panel labs may be used in place of a Day 0 lab draw if acquired within 4 weeks of screening at a Cleveland Clinic lab.

^e Study medication/supplement adherence will be assessed with a pill count. The bottle will be returned to the study site to retain until the end of study.

^f If enrolled for over 14 days and the patient discontinues study medication/supplement perform Day 28 lab work (ITT principle).

^g Historical documented height and weight may be used. Weight to be within the last 3 months. Subject reported is acceptable.

^h Randomization and eligibility confirmation may occur on different days from baseline pending lab results

ⁱ Study medication/supplement will be dispensed by the investigational pharmacy for in person visits to study personnel or shipped to the subjects by the investigational pharmacy following randomization.

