7.1 Discontinuation

7.1.1 Discontinuation of study medication/supplement

Discontinuation of study medication/supplement for a subject occurs when the study medication/supplement is stopped earlier than the protocol planned duration, and can be initiated by either the subject or the investigator.

The investigator must discontinue study medication/supplement for a given subject if, he/she believes that continuation would negatively impact the subject's well-being. After study medication/supplement discontinuation, the patient should remain in the study, unless he/she withdraws consent, preferably in writing.

Study medication/supplement must be discontinued under the following circumstances:

- Subject decision
- Pregnancy
- Any situation in which study participation might result in a safety risk to the subject
- Any laboratory abnormalities that in the judgment of the investigator prevents the subject from continuing study medication/supplement administration

If discontinuation of study medication/supplement occurs, the investigator should make a reasonable effort to understand the primary reason for the subject's premature discontinuation of study medication/supplement and record this information.

Subjects who discontinue study medication/supplement or who decide they do not wish to participate in the study further should NOT be considered withdrawn from the study UNLESS they withdraw their consent. If discontinuation occurs after Day 14, study personnel should attempt to obtain Day 28 labs as close as possible to last dose of study medication/supplement taken.

Where possible, they should return for the Day 28 assessments indicated in the assessment schedule. If they fail to return for these assessments for unknown reasons, every effort (e.g. telephone, e-mail, and letter) should be made to contact the subject/pre-designated contact per institutional guidelines to collect as much data as possible according to the visit schedule.

Patient's vital status can also be verified by the study site upon contact with patient's primary care physician or other sources according to local rules and regulations.

After study medication/supplement discontinuation, at a minimum, in the abbreviated visit, the following data should be collected either during an in person visit or via telephone/email contact:

- new / concomitant treatments
- adverse events/Serious Adverse Events

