#### **4. Study Analysis Sets**

##### **4.1. Full Analysis Set**

The full analysis set (FAS) consists of all enrolled patients. Efficacy variables will be analyzed based on the FAS as the primary population.

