##### **6.1. Missing data**

Missing data will not be imputed unless otherwise specified. Only observed data will be used in the summaries and analyses.

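### Day 28 labs are not firmly required for subjects who stop product by about Day 14, so these subjects can be missing from a primary analysis meant to cover everyone enrolled

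*Protocol*

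**What the plan says.** Several statements bear on what is measured after a subject stops product.

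- **Protocol Table 7-1, footnote f:** "If enrolled for over 14 days and the patient discontinues study medication/supplement perform Day 28 lab work (ITT principle". Nothing is said about a subject enrolled for 14 days or less.
- **Protocol 7.1.1, specific lab sentence:** "If discontinuation occurs after Day 14, study personnel should attempt to obtain Day 28 labs as close as possible to last dose". Nothing is said about a stop at or before Day 14.
- **Protocol 7.1.1, general return sentence:** "Where possible, they should return for the Day 28 assessments indicated in the assessment schedule". It has no day limit and is followed by a commitment to pursue subjects who do not come back.
- **Protocol 7.1.1, minimum data:** "After study medication/supplement discontinuation, at a minimum, in the abbreviated visit, the following data should be collected". The list that follows covers treatments taken and adverse events, and allows telephone or email. It has no blood draw.
- **Protocol 7.1.1, status:** "After study medication/supplement discontinuation, the patient should remain in the study, unless he/she withdraws consent".
- **Protocol section 6:** the text above Table 7-1 states, without a condition, that the lipid panel and hs-CRP are taken at the initial visit and at Day 28.
- **SAP 4.1:** "The full analysis set (FAS) consists of all enrolled patients. Efficacy variables will be analyzed based on the FAS as the primary population".
- **SAP 6.1:** "Missing data will not be imputed unless otherwise specified. Only observed data will be used in the summaries and analyses". SAP 6.3.3 sets the percent change to missing when either value is absent.

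**The concern.** An intention-to-treat analysis needs the outcome of every randomised subject, whether or not product was continued. Here the two specific lab instructions apply only past a 14-day threshold, and how long a subject stays on product is decided after randomisation. People who stop in the first two weeks may do so because of tolerability, which can differ between a statin, a placebo tablet and six supplements. If their LDL-C is not measured, the estimate labelled as applying to all enrolled patients becomes, in part, an estimate among those who persisted past two weeks.

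The plan has no analysis that would show this. The only sensitivity analysis of the primary endpoint (SAP 8.1) uses the per-protocol set of subjects who took at least 80% of product, which moves further from intention-to-treat. Protocol 7.1.1.1 rules out replacement.

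**Working it through.** **1. Passages side by side.** For a subject who stops product on, say, Day 5 and does not withdraw consent:

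| Source | Is a Day 28 draw called for? |
|---|---|
| Footnote f, counting time on product | No instruction |
| Footnote f, read literally (time enrolled) | Yes, once the subject has been enrolled for more than 14 days |
| 7.1.1, specific lab sentence | No instruction (stop not after Day 14) |
| 7.1.1, general return sentence | Yes, if feasible, under a schedule whose Day 28 column carries footnote f |
| 7.1.1, minimum data list | Not listed |
| Section 6 text | Yes |

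The documents therefore neither firmly require nor rule out the draw. For later stops they also differ on timing: footnote f names Day 28 lab work, while 7.1.1 wants the sample close to the last dose. A sample taken soon after a stop just past Day 14 would fall outside the Day 24 to 32 window.

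**2. Consequence in the analysis.** No Day 28 value means a missing percent change (SAP 6.3.3), no imputation (SAP 6.1), and so no contribution to the primary model.

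**3. The plan's own figure.** Inputs from Protocol 4.3.2 and 10.5: SD 15, difference 15, two-sided alpha 0.05, 25 per group, 90% power.

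- Normal approximation: n = 2 × 15² × (1.960 + 1.282)² / 15² = 21.0, so 22 per group. The t-test needs 23.
- Power at 25 per group: Φ(15 / (15 × √(2/25)) − 1.960) = Φ(1.576) = 0.942, or 0.934 by the t-test.

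The stated 25 per group is adequate and slightly conservative.

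**4. Size of the bias.** Let E be the on-product LDL-C lowering and f the fraction who stop early and are not measured, with R for rosuvastatin and C for the comparator. Assume LDL-C is back at baseline by Day 28 in those who stop.

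- Observed-data difference: E_R − E_C
- All-randomised difference: E_R(1 − f_R) − E_C(1 − f_C)
- Overstatement: E_R × f_R − E_C × f_C

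With E_R = 15 and E_C = 0:

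| Rosuvastatin subjects unmeasured | Overstatement | All-randomised difference |
|---|---|---|
| 1 of 25 | 15 × 0.04 = 0.6 | 14.4 |
| 2 of 25 | 15 × 0.08 = 1.2 | 13.8 |
| 3 of 25 | 15 × 0.12 = 1.8 | 13.2 |

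The sign is not fixed. As an illustration, let a comparator lower LDL-C by 15 and rosuvastatin by 15 + 15 = 30, which keeps the planned difference. One unmeasured rosuvastatin subject and two unmeasured comparator subjects give 30 × 0.04 − 15 × 0.08 = 0. With three comparator subjects the result is 1.2 − 1.8 = −0.6, against rosuvastatin.

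**5. Power.** If early stoppers are lost equally from both arms, t-test power for 15 points is 0.924 with one lost per arm, 0.913 with two and 0.900 with three. If three per arm are instead measured and kept, under the step 4 assumptions (E_R = 15, E_C = 0), the rosuvastatin variance becomes 225 × (1 + 0.12 × 0.88) = 248.8. The standard error is √((248.8 + 225)/25) = 4.35, and normal-approximation power is Φ(13.2/4.35 − 1.960) = 0.858. The like-for-like figure with three lost is 0.913.

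**The case against.** A reader might infer that early stoppers are excluded from the primary analysis. The documents do not say that, for four reasons:

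- The general return sentence in 7.1.1 has no day limit, and section 6 states the Day 28 collection without a condition.
- Footnote f counts time enrolled. Because 7.1.1 keeps people who stop in the study, a Day 5 stopper who stays on later meets its condition.
- The minimum data list is a floor for contact that may be by telephone, so leaving out labs does not waive them.
- Nothing in the SAP removes a Day 28 value from an early stopper if one was obtained.

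All of this stands, and it limits the point to subjects who *can* be missing. It does not remove the point. On the literal reading, footnote f excludes nobody who remains to Day 28, so its condition does no work. The neighbouring sentence in 7.1.1 does tie the threshold to the day of the stop. A site could reasonably read the two together and draw no blood.

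A reader might also infer that the bias must favour rosuvastatin. That needs a nearly inactive comparator or more early stopping on rosuvastatin, and the documents establish neither. Protocol 4.3.5 itself allows for more than 15% LDL-C lowering. A larger rosuvastatin effect would scale the figures up in proportion, but the documents give only 15 points.

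**Conclusion.** The concern holds in a limited form. Day 28 labs are not firmly required for subjects who stop by about Day 14. Such subjects can be missing from an observed-data analysis whose population is all enrolled patients and whose schedule invokes the ITT principle.

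The overstatement is 0.6 points for each rosuvastatin subject in 25 left unmeasured. This assumes a 15-point effect, return of LDL-C to baseline after a stop, and a comparator effect near zero. The early-stop rate, its pattern by arm and the speed of return to baseline are not documented, so neither the size nor the direction can be predicted.

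Lost power is not the reason to act. The reason is that whether the primary outcome is measured can depend on an event after randomisation, and a small change to data collection would reduce that.

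**What to change.** Reconcile footnote f and both lab sentences in Protocol 7.1.1 into one data-collection rule: attempt the Day 28 (+4/−4 days) fasting lipid panel, hs-CRP and CMP in every randomised subject who has not withdrawn consent, whenever product was stopped.

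- Delete the 14-day condition from footnote f.
- Align the 7.1.1 sentence on stops after Day 14 with that rule. Left as it is, it keeps the threshold and conflicts with a fixed Day 28 draw.
- Add the Day 28 labs to the data to be sought after a stop in 7.1.1.

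This changes only whether and when blood is drawn, not when product is stopped.

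The cost is a short amendment and a few subjects asked to attend a lab after stopping. The estimated rosuvastatin effect may be slightly smaller, with some loss of power as in step 5 of the working, because the estimate would then describe everyone randomised.
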